Gadoterate (DotaremTM) is a particular Gadolinium agent that has been widely used in Europe for over 24 years and has recently become commercially available in the U.S. Its chemical formulation confers significantly greater stability to the bound state of Gadolinium, compared with other GBCAs (Figure 1) [8-10]. Furthermore, experience based upon widespread clinical use in Europe, as well as data yielded by several smaller studies, strongly indicate that Gadoterate is safe in patients with GFR < 60 and even in patients with GFR < 30 [11-15]. Of note, there have been no cases of NSF in over 43 million administrations in Europe [14], and a German post-marketing analysis of more than 84,000 patients demonstrated no adverse renal events (general adverse events were < 0.3%) despite over 750 patients defined as having a risk factor of chronic renal disease [12]. And, a study of over 500 dialysis patients revealed no cases of NSF after 6 months [15]. It is also important to highlight that even in populations with reduced GFR and end stage renal disease (ESRD) who received serial high-doses of significantly less-stable Gadolinium contrast agents, only a 3-4% rate of NSF has been reported [7,16]. The risk of using a more stable GBCA within strict dosing guidelines is much less. (More generally, there have been an estimated 200 million Gadolinium administrations, with fewer than 1000 cases of NSF). While the risk

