of contrast administration can never be entirely ignored, it is important to be cognizant of these conclusions when considering the suboptimal clinical care often afforded patients who do not receive Gadolinium contrast exams. For example, definitive diagnosis of hepatocellular carcinoma in a patient with cirrhosis, or of renal cell carcinoma in a patient with uncharacterized renal lesions, is all but limited to contrast-enhanced imaging, and manifests in dramatically disparate therapy compared with less definitive diagnosis (therapy initiation vs. serial follow-up imaging or invasive biopsy). Therefore, the benefits of having a GBCA on formulary, with which Gadolinium-enhanced MRI exams could be performed on any patient, regardless of GFR, would be significant to patient-care. The potential scale is significant due to the number of patients that fall into this category in our institution's catchment population as well as across the U.S. [17]. However, widespread misunderstanding of the chemical and clinical data has instilled fear of both medical and legal complications and has precluded current radiology practices from using GBCAs in patients with GFR<30. Currently, we estimate in excess of 800 exams that are annually performed at our institution without Gadolinium enhancement – and thus suboptimally - due to GFR restrictions. Our goal is to therefore gather robust single-site pilot data at Loyola University Medical Center and then proceed to a larger multi-site trial demonstrating the safety and utility of Gadoterate in this particular patient population.

Hypothesis and Study Aims

Hypothesis 1: Use of Gadoterate in a population of patients with GFR<30 will not result in statistically-significant numbers of adverse renal events, defined by decreased GFR and/or NSF.

Hypothesis 2: Use of Gadoterate in a population of patients with GFR<30 will result in more definitive radiologic interpretations and improved clinical care compared with those associated with non-contrast images only. Metrics of evaluation include improved timeliness and quality of disease treatment, as well as fewer follow-up imaging studies with greater specificity (see below).

Specific Aim 1: Establish Gadoterate-based MRI protocols for GFR<30 patients, and establish database (and analytic models) of pre and post-exam laboratory data as well as relevant demographic data.

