To further explore the concept of Gadoterate-based differential outcomes, two separate interpretations for each Gadoterate-enhanced MRI will be recorded in the research database: an interpretation based upon only the non-contrast images and the full interpretation of the whole exam (non-contrast + contrast images). We will subsequently record the *predicted* outcome data, as described above (diagnoses, subsequent imaging studies, pathology results, therapies, and projected related costs), that would be associated with the more limited interpretation of the non-contrast images. Comparison to the actual outcomes of that patient will subsequently be analyzed. This is both feasible and straightforward since the vast majority of the clinical MRI indications in this study have a well-defined diagnostic/therapeutic pathway – i.e. a solitary liver lesion demonstrated to be malignant by contrast MRI would result in chemo-embolization, whereas an indeterminate result based on non-contrast would lead to a liver biopsy [18]. Another example: Cystic renal lesions which cannot be completely characterized without contrast are typically followed with serial imaging exams to check for growth, whereas demonstration of a simple cyst by contrast-enhanced exam will typically result in no further imaging.

Statistics:

Previously-tested GBCAs in chronic kidney failure patients have resulted in 10-25% rates of decreased GFR, depending upon the study, with most investigations recording rates in the range of ~15% [5]. Based upon various data thus far (noted above), the rate is expected to be no more than 5% using Gadoterate;

therefore if we wish to detect a significantly lower rate of renal complications with a power of 90% and a 5% significance, then a sample size of approximately 136 patients receiving Gadoterate is properly powered to address Aim 1. The non-Gadoterate control arm does not need to be as large for analysis of Aim 1, however, it will consist of 136 patients as well, to properly power analysis of Aim 2. This number is expected to be more than sufficient considering that significant interpretive and outcome differentials are anticipated at a far greater rate than 5%, between the non-contrast image and contrast image evaluations.

Study Procedures

Subject selection

Inclusion Criteria: GFR less than 30 ml/min, but not on dialysis, with indications for MRI as described above. GFR will be calculated in the same fashion as in current use in our department:

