Gadoterate will be the only contrast agent used. There is no placebo and no blinding is needed. Gadoterate will be provided by Guerbet pharmaceuticals and will be stored in the identical fashion that all Gadolinium agents are stored in the department (see attached package insert). Gadoterate will be administered according to its standard weight-based protocol, 0.2 mL/kg [8].

Administrative Organization

This will be a single site study conducted at Loyola University Medical Center. Patient recruitment and participation from the referring clinicians in the hepatology, neurosurgery, neurology, neurosurgery, and urology divisions will be coordinated by an MRI nurse coordinator, who will devote 10% time to this project. In addition, all blood draws and patient follow up will be coordinated by the nurse coordinator. All imaging will be conducted on-site. The standard LUMC laboratory locations and procedures will be used to calculate GFR from the patients' serum.

The clinical research office (CRO) will assist with statistical data analysis.

Safety and Monitoring

As with any intravenous contrast agent, numerous nonspecific adverse (mostly allergic-type) reactions are possible, though rare (see attached package insert), for Gadoterate, and no more common than in any other agent in clinical use. The most serious adverse event is difficulty breathing. Patient safety related to

such events will be monitored by direct technician and nurse supervision at the time of the exam and in the immediate period following – this is standard department protocol for all contrast MRI exams.

The main additional serious adverse reaction is the one being specifically monitored in this study - renal toxicity. Monitoring of this will be done by 48-72 hour post-exam serum creatinine evaluation, as described above. In addition, long-term toxicity in the form of NSF will be evaluated by detailed phone follow-up, designed to identify any potential signs of NSF (see Figure 2). In the event of a positive response to 3 or more of the questions in the questionnaire, the patient will be assisted in scheduling a Dermatology appointment at LUMC.

The PI ([name]) and the nurse coordinator will be responsible for tracking and assessing any adverse events.

Reporting of Adverse Events or Unanticipated Problems involving Risk to Participants or Others:

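### Hypothesis 1 pools NSF with decreased GFR and reads non-significance as safety, although the 136 patients were sized on decreased-GFR rates only, so several NSF cases could be consistent with the hypothesis

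*Combined protocol and SAP*

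**What the plan says.** Under Hypothesis and Study Aims, Hypothesis 1 is that use of Gadoterate in patients with GFR below 30 "will not result in statistically-significant numbers of adverse renal events, defined by decreased GFR and/or NSF". It gives no margin, no comparator and no criterion for NSF by itself.

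The Statistics section uses a different criterion, a rate of renal complications significantly lower than with earlier agents. Its reference is "10-25% rates of decreased GFR, depending upon the study, with most investigations recording rates in the range of ~15" percent, and the rate expected with Gadoterate is at most 5%. From these it concludes, "with a power of 90% and a 5% significance, then a sample size of approximately 136 patients receiving Gadoterate", that Aim 1 is covered. The control cohort has the same size for another reason: "it will consist of 136 patients as well, to properly power analysis of Aim 2".

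Aim 1, under Study Design, covers two outcomes: GFR at 48-72 hours, and contacts about NSF at baseline, 6 weeks, 3 months and 6 months. Its analysis sentence promises standard methods for variations in renal function. It names no test or sidedness and does not mention NSF.

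Safety and Monitoring adds that "long-term toxicity in the form of NSF will be evaluated by detailed phone follow-up", with a Dermatology appointment after three or more positive answers. The adverse-event section provides for IRB submission and a 3-monthly review of renal and NSF data by the investigator.

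The Background gives the NSF figures. In populations with reduced GFR and end-stage renal disease, after "serial high-doses of significantly less-stable Gadolinium contrast agents, only a 3-4% rate of NSF has been reported". Overall, it estimates fewer than 1000 cases in 200 million administrations.

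**The concern.** NSF is part of the safety hypothesis and is followed for 6 months, but it enters neither the sample size nor a separate analysis. Its only formal criterion is the pooled one, where a count that does not reach significance supports the hypothesis.

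That criterion has two weaknesses for a rare outcome. First, non-significance with few expected events says little about safety. Second, pooling adds NSF cases to GFR declines, which are expected to be more frequent and which widen the chance variation that an NSF excess must exceed.

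The study could therefore report its safety hypothesis as met with an NSF count in the range the Background cites for less stable agents. With zero cases, the same sentence could be read as evidence on NSF of a strength that 136 patients do not provide. The plan intends these data to lead to a larger multi-site safety trial, so the wording of the conclusion carries forward.

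**Working it through.** **1. The plan's own figure.** Inputs from Statistics: 15% v 5%, power 90%, significance 5%.

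- Two-sample formula, n = [z_α√(2p̄q̄) + z_β√(p₁q₁ + p₂q₂)]² / (p₁ − p₂)², with p̄ = 0.10. Two-sided: (1.960×√0.18 + 1.282×√0.175)² / 0.01 = 187.05, so 188 per arm. One-sided: 153.
- One sample against a fixed 15%, null variance only: (1.960 + 1.282)² × 0.15 × 0.85 / 0.01 = 134, close to 136.

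The standard two-sample formula does not give 136; a simplified one-sample formula comes close. That is a separate matter. What counts here is that every input is a decreased-GFR rate, so no version of the calculation concerns NSF.

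**2. The NSF count that matches the cited rate.** 3% of 136 = 4.08 and 4% of 136 = 5.44. Five is the only whole number between them: 5/136 = 3.7%, exact 95% interval 1.2% to 8.4%.

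**3. The pooled event, as Hypothesis 1 defines it.** The plan gives no control-arm rate of GFR decline. Assume equal numbers of declines per arm, in patients other than the NSF cases, and 5 NSF cases in the Gadoterate arm only. Each arm has 136 patients.

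| GFR declines per arm | Pooled count | Fisher two-sided | Fisher one-sided | Pearson |
|---|---|---|---|---|
| 1 | 6 v 1 | 0.12 | 0.060 | 0.056 |
| 7 (about 5%) | 12 v 7 | 0.34 | 0.17 | 0.23 |
| 14 (about 10%) | 19 v 14 | 0.46 | 0.23 | 0.35 |

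At 7 per arm, Boschloo's test is also non-significant (0.24 two-sided, 0.12 one-sided). At 1 per arm the answer depends on the test: one-sided Pearson gives 0.028 and one-sided Boschloo 0.036.

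**4. The pooled event against the Statistics criterion.** 12/136 = 8.8%. The exact binomial test against 15% gives p = 0.041 two-sided and 0.023 one-sided. The total would count as significantly lower than 15% with five NSF cases in it.

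**5. NSF alone, k v 0 at 136 per arm.**

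| Cases | Fisher two-sided | Fisher one-sided | Pearson |
|---|---|---|---|
| 3 (2.2%) | 0.25 | 0.12 | 0.082 |
| 4 (2.9%) | 0.12 | 0.061 | 0.044 |
| 5 (3.7%) | 0.060 | 0.030 | 0.024 |
| 6 (4.4%) | 0.030 | 0.015 | 0.013 |

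The smallest significant count is 6, 5 or 4, depending on the test. If the true rate were 3% to 4% and no control patient had NSF, the binomial probability of reaching it is 23% to 46% (6 or more), 39% to 64% (5 or more) or 59% to 80% (4 or more).

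**6. Zero cases.** The exact two-sided 95% upper limit is 1 − 0.025^(1/n). For n = 136 it is 2.7%. If 80% complete month 6 (an assumption; 0.8 × 136 = 108.8, so n = 109), it is 3.3%.

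**The case against.** The strongest reply is that no composite analysis is really planned. The pooling rests on one phrase in one hypothesis; elsewhere GFR and NSF are collected and monitored separately, and the Aim 1 analysis mentions only renal function. NSF cases would hardly go unnoticed, given the referral, the IRB reporting and the 3-monthly review. This stands as far as patient protection goes. It does not supply a criterion: none of those steps links an NSF count to the study's conclusion, and the pooled sentence is the only one that does.

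The 3-4% benchmark can also be challenged. It comes from populations including end-stage renal disease, given serial high doses of less stable agents, whereas this study excludes dialysis patients. The Background also cites no NSF in over 43 million European administrations of Gadoterate and none after 6 months in a study of over 500 dialysis patients. So 3-4% is a yardstick from the plan's own text, not an expected rate here. Zero cases in 136 would exclude it, with an upper limit of 2.7%. But the lower the true rate, the less a significance test in 136 patients can say about it.

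A reader might infer that five cases against none would be declared safe, that six are needed for significance, or that 136 per arm cannot register NSF at all. The documents do not support these readings. The first two hold under two-sided Fisher but not under one-sided Fisher or Pearson, and the plan names neither test nor sidedness. On the third, the chance of significance at a true 3-4% is between 23% and 80%, which is limited power but not none.

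Finally, this is a single-site pilot. That limits what should be claimed, which is a reason to word the NSF claim accurately.

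**Conclusion.** The point holds as a defect in a stated criterion and in a stated power property. Hypothesis 1 pools NSF with decreased GFR and treats a non-significant number as safety, while the claim of adequate power for Aim 1 rests on decreased-GFR rates alone.

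As the plan is written, five NSF cases in 136 could be consistent with the hypothesis. This is clearest for the pooled event with about 5% GFR declines in each arm: it is non-significant by every test tried and is even significantly below 15%. That example rests on an assumed control rate and on no overlap between NSF cases and GFR declines. With almost no GFR declines, or with NSF tested alone, five cases may or may not reach significance, depending on the test. Three cases against none are non-significant by both forms of Fisher's test and by Pearson.

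None of this suggests that NSF is likely with Gadoterate. The conclusion is only that the stated criterion is a poor basis for a claim about NSF in either direction.

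**What to change.** In Hypothesis 1 and Statistics:

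- Take NSF out of the pooled significance criterion and keep decreased GFR as the tested component.
- Report NSF separately by cohort. Describe every confirmed case individually, including any in a patient who does not complete month 6. Give the exact 95% interval for the Gadoterate cohort, with patients who completed the 6-month follow-up as denominator.
- State that no conclusion on NSF safety will be drawn from a non-significant p-value.
- With zero cases, report the upper limit for the number actually followed (2.7% if all 136, 3.3% if 109) and say that lower rates are not excluded. Do not fix the percentage in advance.
- Limit the statement of adequate power for Aim 1 to the decreased-GFR component.

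A rule that any single confirmed case defeats the hypothesis is not needed. The exclusion criteria do not bar earlier gadolinium exposure, so one case might not be attributable to the study agent; individual description with an interval lets readers judge.

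The change needs no added patients or procedures. It is a matter of wording, plus a statement by the investigators of what counts as a confirmed case, since the plan describes only the questionnaire and the referral. The downside is a visibly more modest NSF claim.

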Specific Aim 2: Establish database of comparative radiologic findings, clinical care decisions, therapy outcomes, and downstream imaging costs, for radiology interpretations based upon unenhanced vs. Gadoterate-enhanced MRI images.

Study Design

The study design is straightforward, and will consist of 2 equal-sized cohorts of patients, all of whom have GFR of < 30 ml/min, but are not on dialysis, and all of whom are being sent for an MRI examination in the course of routine clinical evaluation of one of the following indications: suspected or known head/neck/brain mass, hepatic mass, renal mass, pancreatic mass, or prostate mass, as well as evaluation of carotid or abdominopelvic vasculature. These relatively few indications constitute the vast majority of indications for contrast MRI in our health system, similar to most institutions. As such, there will be significant statistical representation of these indications in each cohort. At the same time, limiting the study to these indications will allow greater organizational structure, with more focused points of enrollment. Note that each of the corresponding clinical departments has expressed significant interest in participation; patients will be enrolled over a two year period from the hepatology, surgery, urology, neurology, and neurosurgical services at Loyola. Following IRB approval and informed consent, patients in the first group will receive MRI exams with no Gadolinium contrast, while the other group will receive standard pre-contrast *and* Gadoterate-enhanced acquisitions (0.2 mL/kg). MRI protocols utilized in the study will be comprised of the standard Body protocols (routine abdomen, liver-pancreas, renal, prostate,

angiography) as well as the standard Neurologic exam protocols (routine brain, orbital, brainstem, neck, angiography).

Ineligibility criteria will include pregnancy, lactation, planned initiation of chemotherapy or surgery within 72 hours of the MRI exam, hemodynamic instability or acute coronary syndrome, history of nephrotoxic medication within 2 weeks of the exam (Amphotericin B, Lithium, Pentamidine, Aminoglycosides, Acyclovir, Gancyclovir, or Foscavir), and age less than 18 years.

Aim 1:

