In reviewing the radiology informatics system, the coordinator may identify a patient who meets eligibility criteria and whose GFR has already been obtained through standard care, but who already had a standard MRI completed without contrast within the past 24 hours. If this occurs, the PI will be notified to determine if it is appropriate to contact the patient and obtain consent post-MRI. If the patient consents

to the study, they would be placed into the control (non-contrast) group and undergo the remaining study activities of post-MRI blood draw and questionnaires at baseline, 6 weeks, 3 months and 6 months.

Consent

A discussion of the study, including discussion of risks and benefits, will be conducted by the study staff (PI, sub-investigator, research nurse, or study coordinator) with the patient at least 8 hours prior to the exam (except, as noted above, in the event a patient is identified post-exam). The consent form can then be signed at the time of the exam. Consent will be obtained following our institution's policies and procedures. Patient eligibility will be confirmed prior to study enrollment.

If a patient is unable to give informed consent due to cognitive dysfunction (for example, stroke, trauma, or encephalopathy from liver failure), their guardian, spouse, parent, or the individual holding power of attorney for their healthcare will be approached to consent for the patient. If the patient regains his or her ability to make decisions, he or she will be informed about the study and asked for a decision about continued participation. In the event the patient does not regain his or her ability to make decisions at the time the questionnaires are administered, the individual who consented on behalf of the patient will be asked to answer the symptom questionnaires on the patient's behalf.

Recruitment materials

No advertising will be provided. Written material will consist of the ICD. \$25 will be provided to patients as compensation for their 2-3 day return visit (blood-draw) and \$5 for parking.

Selection

It is expected that a significant percentage of patients fulfilling the eligibility criteria will nevertheless choose to decline receiving Gadoterate and receive the default non-contrast exam. These patients will be asked to take part as the non-contrast arm of the study.

Gadoterate

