Any adverse events, as described above or unanticipated, involving risk to participants, will be promptly submitted to the IRB in accordance with established guidelines.

In addition, all data related to renal function and NSF will be routinely reviewed by the PI every 3 months.

Analysis

Image analysis: As described above, each MRI exam will be independently interpreted by 2 participating sub-specialty-trained (either neuro or body) radiologists, with the readers blinded to history and prior exams. For both contrast and non-contrast exams, the images will be viewed in the standard clinical fashion (Intellispace PACS system). For the contrast exams, the interpreting radiologists will first render an evaluation based upon *only* the non-contrast images - these interpretations will be recorded only within the research database. As described earlier, this will enable evaluation of the added advantages of the contrast agent. The overall contrast-exam interpretations, as well as the interpretations of the non-contrast exams, will be recorded in both the research database as well as dictated into the EMR, since these studies will be ordered as part of clinical care. The CRO will assist in analyzing trends of inter-reader correlation and variability.

Outcomes analysis: We will analyze the differential outcomes, between the two cohorts, as well as between the projected and actual outcomes within the contrast cohort, in these specific categories: diagnoses, number and types of subsequent imaging studies, pathology results, therapies, and related costs (defined as gross hospital charge), within the study period and extending 1 year afterward. The CRO will assist in analyzing variation within these metrics between the non-contrast vs. contrast cohorts. The CRO will also assist in analysis of variation between the projected outcomes and actual outcomes within the contrast cohort.

Risks vs Benefits

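### The between-cohort comparison in Aim 2 spans seven indications in self-selected cohorts without stratifying or adjusting for indication, so a difference in mix can appear as a contrast effect.

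*Combined protocol and SAP*

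**What the plan says.** Study Design lists the eligible indications: masses of the head/neck/brain, liver, kidney, pancreas and prostate, and evaluation of the carotid or abdominopelvic vessels. That is seven, counting head/neck/brain as one. Because these few make up most contrast MRI at the site, the section concludes: "As such, there will be significant statistical representation of these indications in each cohort".

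The cohorts are not randomised. Under Selection, the protocol expects that "a significant percentage of patients fulfilling the eligibility criteria will nevertheless choose to decline receiving Gadoterate", and those patients are invited to form the non-contrast arm. Under Recruitment, some controls may be consented within 24 hours after a completed non-contrast scan. Patients found through a non-contrast order need an updated order from their physician before they can receive contrast.

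The outcomes analysis, under Analysis, states: "We will analyze the differential outcomes, between the two cohorts, as well as between the projected and actual outcomes within the contrast cohort". The categories are diagnoses, subsequent imaging, pathology, therapies and gross hospital charges. Neither this section nor the Aim 2 text in Study Design mentions stratification, matching or adjustment by indication. Under Statistics, the size of the control cohort is justified by Aim 2: "it will consist of 136 patients as well, to properly power analysis of Aim 2".

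**The concern.** A short list of indications makes it likely that the common ones occur in both cohorts. It does not make their shares equal. Where patients and their physicians decide who receives contrast, the shares can differ systematically, and a larger sample does not remove such a difference.

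The downstream outcomes plausibly vary with indication. The Aim 2 text gives two examples: a solitary liver lesion leads to chemo-embolization or biopsy, while a cystic renal lesion leads to serial imaging or none. If one cohort holds more liver patients and the other more renal patients, imaging counts, therapies and charges could differ even if contrast changed nothing.

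At stake is the comparison for which the 136 controls are enrolled, and one half of the evidence for Hypothesis 2. There is also a smaller cost: even with a balanced mix, leaving indication out of the analysis puts its variance into the error term.

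**Working it through.** **The plan's own figure.** The protocol gives 136 per cohort. It comes from Aim 1 (15% against 5%, 90% power, 5% significance) and is carried over to the controls. For two equal groups, the usual normal-approximation formula gives 188 per group two-sided and 153 one-sided, so 136 is not reproduced at 90% power. It is close to the two-sided result at 80% power (138 with unpooled variance, 133 by arcsine). That is a separate matter, and nothing below depends on it. For Aim 2 there is no figure to reproduce, because no endpoint, rate, standard deviation or difference is stated.

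**Inputs.** From the documents: 136 per cohort, seven indications, cohorts formed without randomisation. Every other input below is assumed.

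**1. Patients per indication.** With equal shares, 136 / 7 = 19.4 per indication per cohort. Power for 50% against 30% is then about 24% within one indication, against 92% in the full cohorts. Results must therefore be combined over indications, not read one at a time.

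**2. Bias in mean charges.** Let a share p of a cohort have indications with r times the charges of the rest. The relative mean is p × r + (1 − p). Take p = 40% in one cohort and 30% in the other, with no contrast effect.
- r = 3: 1.8 / 1.6 = 1.125, a difference of 12.5%.
- r = 5: 2.6 / 2.2 = 1.182, a difference of 18.2%.

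To set this against sampling error, let R² be the share of charge variance explained by this two-group split. The bias is 0.10 × (r − 1). The total SD is √(0.35 × 0.65) × (r − 1) / √R², taking the average share of 35%. The standard error is that SD × √(2/136). The factor r − 1 cancels, so bias / SE = 0.10 × √R² / (0.477 × 0.1213) = 1.73 × √R².

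| R² | Bias / SE | Two-sided rejection at nominal 5% |
|---|---|---|
| 10% | 0.55 | 8% |
| 20% | 0.77 | 12% |
| 30% | 0.95 | 16% |

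**3. Bias in a proportion.** Suppose some indications lead to further imaging in 60% of patients and the others in 20%, with no contrast effect. The standard error is √[(p₁(1 − p₁) + p₂(1 − p₂)) / 136]. For a mix of 60/40 against 40/60, p₁ = 0.44, p₂ = 0.36 and SE = 0.0592, so the ratio is 0.08 / 0.0592 = 1.35.

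| Mix in the two cohorts | Difference, rates 60% and 20% | Rejection | Difference, rates 50% and 30% | Rejection |
|---|---|---|---|---|
| 55/45 and 45/55 | 4 points | 10% | 2 points | 6% |
| 60/40 and 40/60 | 8 points | 27% | 4 points | 10% |
| 65/35 and 35/65 | 12 points | 53% | 6 points | 17% |

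**4. Precision.** With a balanced mix, the unadjusted standard error is 1/√(1 − R²) times the adjusted one, and adjusting is worth 136 / (1 − R²) patients per cohort.

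| R² | SE ratio | Equivalent patients per cohort |
|---|---|---|
| 10% | 1.05 | 151 |
| 20% | 1.12 | 170 |
| 30% | 1.20 | 194 |

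A mix of 60/40 against 40/60 takes back about 4% of this (1 − 0.2² = 0.96), leaving about 145 to 187.

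**The case against.** The strongest reply is that the plan does not prescribe a pooled analysis. It says that the clinical research office will help to analyse variation in these metrics, and it keeps the outcome categories separate. Pooling over indications is inferred from the absence of any indication term. That is fair. But the stated contrast is between the two cohorts, and an analyst who followed the text would have no instruction to stratify.

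Second, half of Aim 2 escapes the problem. In the Gadoterate cohort, each patient's predicted outcome from the non-contrast images is compared with that patient's actual outcome, so indication mix cannot confound it. This stands. It does not replace the cohort comparison, because it rests on predicted outcomes.

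Third, the Study Design sentence claims representation, not equal shares, and nothing in the documents shows it to be false. This also stands. The difficulty is that the sentence is the only safeguard offered and does not do that work.

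Fourth, this is single-site pilot work, and indication is only one part of self-selection. Both are true. Hypothesis 2 is nevertheless comparative, and indication is a part that can be removed at little cost.

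A reader might go further and infer that these outcomes depend on indication more than on contrast. The documents do not support that. The liver and renal examples contrast pathways within an indication according to the imaging result, and no charges or rates by indication are given.

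**Conclusion.** The point holds for the between-cohort part of Aim 2. Its cohorts are self-selected, span indications with different pathways, and are to be compared without stratification or adjustment by indication. A difference in mix can then be read as an effect of contrast.

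The size and direction cannot be taken from the documents. On the assumed inputs above, the spurious difference is about 12% to 18% in mean charges, with a false-positive rate of roughly 8% to 16%. For a proportion it is 2 to 12 percentage points, with a false-positive rate of 6% to 53% depending on the mix and the rates. Adjusting is worth about 151 to 194 patients per cohort instead of 136. Merging indications into fewer groups would tend to reduce that gain.

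Three stronger readings should not be drawn. Aim 2 as a whole is not confounded by mix, since the within-patient comparison is unaffected. Imbalance is not shown to occur; it is only left unguarded. And a gain as large as 136 / 0.5 = 272 patients per cohort would need indication to explain half of the outcome variance, which nothing in the documents supports.

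**What to change.** In the outcomes analysis under Analysis:
- Tabulate indication by cohort.
- State that each between-cohort Aim 2 comparison is stratified by, or adjusted for, indication, merged into 3 or 4 groups fixed before outcomes are examined.
- Use one common weighting for proportions, counts and charges, for example standardisation to the Gadoterate cohort's mix, so that all outcomes refer to the same population. Mantel-Haenszel weights for proportions alone would not meet this, because they are not the Gadoterate cohort's shares.

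In Study Design, state that representation of the indications does not ensure balance and that the analysis adjusts for indication.

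The cost is analysis wording and one table. Indication is already established at eligibility and by the MRI protocol used, so no visit, patient or recruitment rule changes. The downsides are that rare indications must be merged, which leaves some mix difference within groups, and that other differences due to self-selection remain.
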